#### Listing 16.2.1.11 Medications – Enrolled Set

All medications, prior, concomitant and subsequent, will be listed for patients in the enrolled set.

## Listing 16.2.1.12.1 L-DOPA/DDCI Medications – Enrolled Set

L-DOPA/DDCI medications will be listed for patients in the enrolled set.

## Listing 16.2.1.12.2 Change of L-DOPA/DDCI Medications – Safety Set

L-DOPA/DDCI adjustment will be listed for patients in the safety set.

## 5.4 Exposure to IP and Rescue Medication and Compliance

## 5.4.1 Exposure to IP

Exposure data from eCRF include:

- Date/ Time of the first IP intake
- Date of last IP intake
- Start/ Stop interruption date
- IP interruption cause (AE number)

Following information will be delivered by IWRS provider:

- Kit no.

I-DM-011SAP Page 22 of 49

- Number of dispensed/ returned IP capsules

## 5.4.2 IP Compliance

Treatment compliance will be calculated as:

Overall compliance (%) = 
$$\frac{(N \ of \ capsules \ dispensed - N \ of \ capsules \ returned)}{Overall \ treatment \ duration} \times 100$$

**Post-BDRM note**: The listing of all subjects who lost at least one IP kit including explanation and decision can be found in Appendix 3. This appendix will be used to correct drug accountability data.

If from the explanation presented in the PD log/ query it is not possible to identify the lost number of capsules, compliance will not be calculated. In case a subject discontinued the study due to lost to follow-up reason, lost kits will be counted as not used.

Compliance will be categorised as:

- < 80%
- $\geq 80\%$  and  $\leq 120\%$
- > 120%
- Missing

The following statistical output will be provided:

I-DM-011SAP Page 23 of 49

Table 15.1.12.2.1 Treatment Compliance – Safety Set

Table 15.1.12.2.2 Treatment Compliance – Full Analysis Set

Table 15.1.12.2.3 Treatment Compliance – Per-Protocol Set

The default summary statistics of compliance will be presented by treatment group and overall. The number and percentage of patients within each compliance category ( $< 80\%, \ge 80\%, \le 120\%, > 120\%$ and Missing) will also be summarised. Percentages will be based on the number of patients in the corresponding analysis set.

## Listing 16.2.2.1 Exposure to IP and Treatment Compliance – Safety Set

Drug accountability data as well as their overall compliance will be displayed for each patient in the safety set.

#### 5.4.3 **Exposure to Rescue Medication**

The rescue medication (paracetamol or tramadol) will be dispensed at Visit 2b, Visit 4 and Visit 5.

Following information will be delivered by IWRS provider:

- Type of rescue medication
- Number of dispensed/ returned rescue medication tablets/ capsules

Detailed description of usage of rescue medication is provided in Section 5.5.2.8.

The following statistical output will be provided:

Listing 16.2.2.2 Exposure to Rescue Medication – Safety Set

Drug accountability of rescue medication data will be displayed for each patient in the safety set.

## **Efficacy Analysis**

Efficacy analysis of the primary endpoint will be based on the FAS and PPS (under MAR assumption for primary evaluation and MNAR for sensitivity purposes). The efficacy of the secondary endpoints will be based on the FAS and PPS.

#### 5.5.1 **Primary Efficacy Analysis**

The King's Parkinson's Disease Pain Scale (KPPS) evaluates the burden (global and bedside) and characterises various phenotypes of pain in PD. Its seven domains include 14 items, each item scored by severity (0-3) multiplied by frequency (0-4), resulting in subscores of 0 to 12. The total possible KPPS score (0 to 168) represents the symptomatic burden by pain. The questionnaire will be fill out on Visit 1, Visit 2b, Visit 4, Visit 5 and Visit 6/EDV.

The primary efficacy endpoint of this study is the change from baseline to Visit 6/EDV in the Domain 3 of KPPS. The Domain 3 is about fluctuation-related pain and consists of 3 questions and the total possible Domain 3 score ranges from 0 to 36. The primary efficacy endpoint will be analysed using a two-sided alpha 0.05 using a mixed model for repeated measures (MMRM) assuming the unobserved data is missing at random (MAR) to demonstrate differences in the fluctuation-related pain score between opicapone 50 mg and placebo in addition to current treatment with L-DOPA/DDCI for PD patients with end-of dose motor fluctuations and associated pain.

The following statistical hypotheses will be tested:

$$H_0$$
:  $\mu_T = \mu_C$ 

$$H_1$$
:  $\mu_T \neq \mu_C$ 

where  $\mu_T$  is mean change in Domain 3 of KPPS from baseline in the opicapone treatment arm and  $\mu_C$  is mean change in Domain 3 of KPPS from baseline in the placebo arm. For the rational used under the sample size and hypotheses see section 2.6.

Only subjects without missing baseline score will be used for analysis using MMRM. The MMRM is longitudinal approach which analyse data as collected (including missing values). Analyses will include the fixed, categorical effects of treatment, visit, and treatment-by-visit interaction, as well as the

I-DM-011SAP Page 24 of 49

continuous, fixed covariates of baseline score. The two-sided test estimated results with alpha level of 0.05 will be provided.

An unstructured variance structure will be used to model the within-patient errors. If this analysis fails to converge, the following structures will be tested in order defined below until model convergence is reached:

- Heterogeneous Toeplitz
- Heterogeneous autoregressive
- Toeplitz
- Autoregressive
- Compound symmetry
- Variance components

The Kenward-Roger approximation will be used to estimate degrees of freedom.

Following SAS code will be used to fit MMRM model:

```
PROC MIXED DATA = <DATASET>;
    CLASS <TREATMENT> <VISIT> <SUBJECT ID>;
    MODEL <CHANGE FROM BASELINE> = <TREATMENT> <VISIT> <BASELINE>
<TREATMENT>*<VISIT> / S DDFM=KENROG;
    REPEATED <VISIT> / TYPE=<UN> SUBJECT=<SUBJECT ID>;
    LSMEANS <TREATMENT>*<VISIT> / CL PDIFF;
RUN;
```

Moreover, exploratory analysis of each subgroup as defined in Section 3.2 will be performed. The primary model as described above will be used by each subgroup. In addition, forest plots will be generated representing the difference of LS Means and corresponding 95% CI.

For sensitivity purposes, missing data for the primary efficacy endpoint will be imputed using MI under the missing not at random (MNAR) assumption by creating control-based pattern imputation, assuming that those subjects who have missing data will behave as if they were taking placebo (worst-case scenario). The missing efficacy endpoint data at Visit 4, Visit 5, Visit 6 will be imputed using pattern mixture models. The regression method will be used which fits a regression model. Based on the fitted regression model, a new regression model is simulated and used to impute the missing values for each variable. The number of imputations will be at least 100.

The variables to be used in the MI are treatment, baseline score, and observed values at appropriate visits. Observations from the placebo group will be used to impute the missing data.

The following SAS code will be used for imputations:

```
PROC MI DATA=<DATASET> SEED=14442 NIMPUTE=100 OUT=<OUTPUT DATASET>
    ROUND =. . 1 1 1
    MINIMUM =. . 0 0 0
    MAXIMUM =. . 36 36 36;
    CLASS <TREATMENT>;
    FCS REG(/ DETAILS);
    MNAR MODEL (<VISIT 4> <VISIT 5> <VISIT 6> /
MODELOBS=(<TREATMENT>="PLACEBO"));
    VAR <BASELINE VALUE> <VISIT 4> <VISIT 5> <VISIT 6>;
RUN;
```

The MMRM model described earlier will be applied to each of the imputed datasets, and the resulting least squares (LS) means/LS means differences and including their respective standard errors will be aggregated and further evaluated using the following SAS statements:

```
PROC MIANALYZE DATA = <DATASET>;
          MODELEFFECTS <LS MEAN ESTIMATES/LS MEAN DIFFERENCE ESTIMATES>;
          STDERR <LS MEAN STANDARD ERRORS/LS MEAN DIFFERENCE STANDARD ERRORS>;
RUN:
```

I-DM-011SAP Page 25 of 49

Additional sensitivity analysis of rescue medication impact to the primary efficacy endpoint will be performed. MMRM model will be used for analysis. Details will be specified during BDR meeting.

**Post-BDRM note**: It was decided that sensitivity analysis of rescue medication impact to the primary efficacy endpoint will be conducted if more than 10% of subjects were using tramadol during the last 30 days prior to the primary endpoint. As in total only 12 subjects used tramadol 30 days before V6/EDV the sensitivity analysis will not be performed as 12 out of 122 subjects correspond to 9.8%.

The following statistical output will be provided:

Table 15.2.1.1.1 Summary of KPPS – Full Analysis Set

Table 15.2.1.1.1.2 Summary of KPPS – Per-Protocol Set

The KPPS domains and total scores will be summarised by visit, including changes from baseline, using default summary statistics.

Table 15.2.1.1.2.1 Summary of the Domain 3 of KPPS by Subgroup – Full Analysis Set

Table 15.2.1.1.2.2 Summary of the Domain 3 of KPPS by Subgroup – Per-Protocol Set

The KPPS domain 3 score will be summarised using default summary statistics by each subgroup and visit, including changes from baseline.

Table 15.2.1.2.1.1 Analysis of the Domain 3 of KPPS – Full Analysis Set

Table 15.2.1.2.1.2 Analysis of the Domain 3 of KPPS – Per-Protocol Set

Table 15.2.1.2.2.1 Analysis of the Domain 3 of KPPS (MI) - Full Analysis Set

Table 15.2.1.2.2.2 Analysis of the Domain 3 of KPPS (MI) - Per-Protocol Set

Table 15.2.1.2.3.1 Analysis of the Domain 3 of KPPS by Subgroup – Full Analysis Set

Table 15.2.1.2.3.2 Analysis of the Domain 3 of KPPS by Subgroup – Per-Protocol Set

The LS means associated with treatments and treatment differences will be presented with 95% confidence intervals and corresponding p-value for each visit for the Domain 3 of KPPS.

Figure 15.2.1.1 Domain 3 of KPPS Change from Baseline LS-Means by Visit – Full Analysis Set

Figure 15.2.1.2 Domain 3 of KPPS Change from Baseline LS-Means by Visit – Per-Protocol Set

A line chart with error bars will be used to display the LS-means and 95% confidence intervals.

Figure 15.2.2.1 Forest Plot of Domain 3 of KPPS by Subgroup – Full Analysis Set

Figure 15.2.2.2 Forest Plot of Domain 3 of KPPS by Subgroup – Per-Protocol Set

Forest plots will be used to display difference of LS Means and 95% CI for Visit 6 by each subgroup. Primary model difference of LS Means, and 95% CI will be included as well.

Listing 16.2.3.1 KPPS – Enrolled Set

KPPS data and total score will be displayed for each patient in the enrolled set.

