## 2.6 Sample Size

For the primary endpoint (change from baseline in Domain 3 of KPPS), a difference to placebo of 3.0 is regarded as clinically meaningful and from a former study (Rascol O et al 2016; DOI: 10.1002/jcph.678) a standard deviation of 5.8 can be assumed in both arm groups. With a two-sided significance level  $\alpha$  of 0.05, a power of 80%, a 1:1 treatment allocation ratio and with the abovementioned assumptions,  $2 \times 60 = 120$  evaluable patients are required. An approximate drop-out rate of 15% is assumed, therefore 140 patients need to be randomised.

**Post-BDRM note**: 144 patients were screened and 127 were randomised. Sample size differs from planned because study was early terminated. As the drop-out rate was less than 15%, the early termination will not have an impact. A total of 120 evaluable patients were required and 122 subjects belong to the full analysis set.

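### The primary MMRM holds the baseline slope equal across visits and omits the Visit 1 Domain 3 score, which probably costs a little precision at Visit 6

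*SAP*

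**What the plan says.** SAP Section 5.5.1 fits an MMRM to change from baseline in Domain 3, with treatment, visit, treatment-by-visit and "continuous, fixed covariates of baseline score". The code agrees with the text: "MODEL <CHANGE FROM BASELINE> = <TREATMENT> <VISIT> <BASELINE>", followed by the treatment-by-visit term and nothing else. The covariance is unstructured if it converges, with Kenward-Roger degrees of freedom. The endpoint is the change to Visit 6.

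On data collection, the same section says: "The questionnaire will be fill out on Visit 1, Visit 2b, Visit 4, Visit 5 and Visit 6/EDV". Domain 3 is an entry criterion at both Visit 1 and Visit 2b (protocol synopsis, inclusion criteria 10 and 15). Under SAP Section 4.7 the baseline is the last non-missing value before first intake, so normally Visit 2b. The Visit 1 score enters neither the MMRM nor the VAR list of the imputation code.

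The protocol synopsis planned an ANCOVA of the change to Visit 6 with one baseline covariate. SAP Section 8 records the switch to MMRM but does not mention the baseline slope.

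**The concern.** A main effect for baseline forces the same slope at Weeks 4, 12 and 24. If the correlation with baseline fades over time, the fitted slope is a compromise between visits and need not be the best one for Visit 6. The protocol's ANCOVA estimated a Visit 6 slope by construction, so the restriction arrived with the change of model, and the SAP gives no reason for it. The SAP's own imputation step regresses each visit variable separately, so it lets the baseline coefficient differ by visit; the MMRM then fitted to the imputed data does not.

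The Visit 1 score is a second pre-randomisation reading of the same quantity, expected for nearly every randomised patient because it decides eligibility. Averaging over two noisy readings usually predicts the outcome better than one.

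At stake is the width of the Visit 6 confidence interval, not the validity of the test. The same structure is reused for the secondary MMRMs (Section 5.5.2) and the subgroup fits (Section 3.2).

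**Working it through.** **1. The plan's own figure.** Inputs from SAP Section 2.6: "a difference to placebo of 3.0 is regarded as clinically meaningful"; "a standard deviation of 5.8 can be assumed in both arm groups"; "a power of 80%, a 1:1 treatment allocation ratio"; two-sided alpha 0.05.

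n per arm = 2(1.960 + 0.842)² × 5.8² / 3.0² = 2 × 7.849 × 33.64 / 9 = 58.7, so 59 by the normal approximation. The exact t calculation gives 60, which is the stated 2 × 60 = 120. For drop-out, 118/0.85 = 138.8 and 120/0.85 = 141.2, which bracket the stated 140. The calculation contains no covariate term, so the planned power does not depend on how baseline is modelled.

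**2. Cost of the common slope (large sample, complete data).** Let β be the vector of slopes of the Domain 3 score on baseline at the three visits, S the residual covariance, 1 a vector of ones and σ₆² the Visit 6 residual variance. The common slope converges to b = 1'S⁻¹β / 1'S⁻¹1. The proportional excess variance at Visit 6 is (β₆ − b)² × Var(baseline) / σ₆². Modelling change instead of score lowers every slope by 1 and leaves β₆ − b unchanged.

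The documents give no correlations. The examples below assume SD 5 at baseline and 6 afterwards; b also depends on the assumed correlation between follow-up visits.

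| Correlation with baseline at V4, V5, V6 | Slopes | b | Excess variance at V6 |
|---|---|---|---|
| equal slopes | equal | equal | 0% |
| 0.6, 0.5, 0.4 | 0.72, 0.60, 0.48 | 0.628 | 0.148² × 25 / 30.24 = 1.8% |
| 0.7, 0.5, 0.3 | 0.84, 0.60, 0.36 | 0.714 | 0.354² × 25 / 32.76 = 9.6% |
| 0.7, 0.45, 0.2 | 0.84, 0.54, 0.24 | 0.720 | 0.480² × 25 / 34.56 = 16.7% |

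Here σ₆² = 36(1 − r²), with r the Visit 6 correlation.

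**3. Value of the Visit 1 score (large sample).** Let r₂ be the correlation of Visit 2b with Visit 6, r₁ that of Visit 1 with Visit 6, and r_s that of Visit 1 with Visit 2b. Then R² = (r₁² + r₂² − 2r₁r₂r_s)/(1 − r_s²), and the variance falls by 1 − (1 − R²)/(1 − r₂²). For r_s = 0.7, r₂ = 0.5 and r₁ = 0.45: R² = (0.2025 + 0.25 − 0.315)/0.51 = 0.270, and the fall is 1 − 0.730/0.75 = 2.6%. Over r_s 0.6-0.9, r₂ 0.3-0.6 and r₁ at 0.8-1.0 times r₂, the fall runs from 0 to 14%.

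**4. At the actual size.** Large-sample figures ignore the cost of estimating extra slopes. Five scenarios of 4,000 simulated trials each used 122 patients, complete data, scores from 0 to 36 and a minimum of 12 at both pre-treatment visits. (The SAP gives at least 12 at Visit 2b; the protocol synopsis prints more than 12.) The last two columns show the change in the variance of the Visit 6 treatment difference against the planned model.

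| r_s | r₂ | Free slope | Free slope plus Visit 1 |
|---|---|---|---|
| 0.60 | 0.45 | +0.4% | −3.9% |
| 0.45 | 0.35 | +0.4% | −3.8% |
| 0.67 | 0.35 | −1.2% | −2.0% |
| 0.49 | 0.28 | −0.3% | −3.0% |
| 0.45 | 0.17 | −1.7% | −2.3% |

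A second 122-patient simulation under other assumed correlations gave +0.2% to −8.9% for the free slope and −1.8% to −9.4% with Visit 1 added.

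**5. In terms of power.** At 61 per arm (122 in the full analysis set), treating 5.8 as the residual SD under the planned model, SE = 5.8√(2/61) = 1.050. Power is then Φ(3.0/1.050 − 1.960) = 81.5% by the normal approximation. With 2% less variance it is 82.3%, and with 4% less 83.0%. With 5% less, SE = 1.050√0.95 = 1.024 and power is 83.4%.

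**The case against.** The strongest reply is that nothing here is an error. The SAP pre-specifies a standard baseline-adjusted MMRM, its text and code agree, and it keeps the protocol's single baseline covariate. A richer covariate set is a preference, and its benefit rests on correlations that the documents do not give. If the slopes are equal, freeing them gains nothing and at 122 patients may cost a fraction of a percent. All of that stands.

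It is also fair that the change takes more than one line. A patient without a Visit 1 score would drop out of the model. If Visit 1 has to serve as baseline, the same number would enter twice. The imputation model would need to match. Six baseline parameters in place of one is a lot for each of the ten subgroup-level fits. The SAP was finalised after blind data review, and its primary model had already been changed once, so a further change has some cost in credibility. These points shape the fix; each is met by a short rule.

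The early stop does not strengthen the concern. Section 2.6 reports 127 randomised instead of 140, but also 122 in the full analysis set against 120 required.

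**Conclusion.** This is a missed efficiency of minor importance. The model structure is plain from the SAP; the size of the loss is not, because every correlation used is assumed. Under those assumptions the free slope alone is worth between nothing and a few percent of the Visit 6 variance. Larger gains, such as the 10-17% in the steep cases above, need the baseline correlation to fall from about 0.7 to 0.2-0.3. With the Visit 1 score added, a gain of about 2-5% is typical, or roughly 1-2 points of power, and most of it usually comes from the Visit 1 score.

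Three stronger readings are tempting and unsupported:

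- A reader might infer that the fitted slope is wrong for Visit 6. That requires slopes that differ by visit, which the documents do not show.
- A reader might infer that precision is given up for no reason, or could be had back free. Extra parameters and a further change to the primary model are real, if small, costs.
- A reader might infer bias or an underpowered trial. With complete data the randomised comparison is unbiased under a common slope, and the 80% calculation uses no covariates. The documents do not say how many patients lack Visit 6, so nothing can be concluded here about bias from missing data.

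**What to change.** Before unblinding, issue a dated SAP revision with an entry in Section 8:

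- **Primary MMRM:** treatment, visit, treatment-by-visit, baseline Domain 3, baseline-by-visit, Visit 1 Domain 3 and Visit 1-by-visit. Fit the same model to the imputed data sets.
- **Secondary MMRMs:** add baseline-by-visit. MDS-NMS, MDS-UPDRS and PDQ-8 are first recorded at Visit 2b, so they get nothing more. KPPS total and Domain 4 do have a Visit 1 score, so state whether it is used.
- **Missing Visit 1 score:** fill it by a simple rule that ignores treatment, for example the overall Visit 1 mean, so that no patient is dropped. Apply the same rule to the Visit 1 covariate when Visit 1 has to serve as baseline.
- **Imputation:** add Visit 1 to the VAR list and keep the rounding and range lists in step with it.
- **Subgroups:** keep the simpler model.
- **Sensitivity:** report the current primary model alongside.

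The cost is a few lines of text and code, five more model parameters, a possible trivial loss if the slopes are in fact equal, and one more documented change to the primary model after blind data review. No new data are needed. If the code has already been released, the richer model can serve only as a labelled post hoc sensitivity analysis.

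### The pooling step of the MI sensitivity analysis supplies no complete-data degrees of freedom, so its intervals and p-values use near-normal quantiles while the MMRM uses Kenward-Roger (a minor mismatch)

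*SAP*

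**What the plan says.** SAP section 5.5.1 sets the primary test as follows: "The primary efficacy endpoint will be analysed using a two-sided alpha 0.05", with an MMRM. On its reference distribution the text says: "The Kenward-Roger approximation will be used to estimate degrees of freedom". The model code agrees (`DDFM=KENROG`).

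For sensitivity, the same section imputes missing KPPS Domain 3 scores from the placebo group (`NIMPUTE=100`; the text asks for at least 100), refits the MMRM to each completed dataset, and pools the LS means and their differences. The pooling code opens with "PROC MIANALYZE DATA = <DATASET>" and has two further statements, one naming the estimates and one naming their standard errors. It has no `EDF=` option. No other text in the SAP sets complete-data degrees of freedom for the pooled test. The output list in the same section promises 95% confidence intervals and p-values by visit, and the MI tables are planned for both the full analysis set (FAS) and the per-protocol set.

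**The concern.** When PROC MIANALYZE receives no complete-data degrees of freedom, it takes them as infinite and applies Rubin's large-sample formula. That is how the software behaves; the SAP does not state it. The Kenward-Roger degrees of freedom from each fitted MMRM are then lost at pooling, and the pooled analysis claims more degrees of freedom than any single completed dataset could supply, which is incoherent.

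What is at stake is comparability. A sensitivity analysis should differ from the primary analysis through its missing-data assumption alone. Here part of the difference in interval width and p-value would come from an unstated software default, and that default is the more lenient reference, although the SAP presents the placebo-based assumption as a worst case.

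**Working it through.** **Inputs from the documents**
- m = 100 imputations (SAP 5.5.1).
- FAS size, SAP 2.6: "A total of 120 evaluable patients were required and 122 subjects belong to the full analysis set".
- Standard deviation, SAP 2.6: "a standard deviation of 5.8 can be assumed in both arm groups".
- Target difference, SAP 2.6: "a difference to placebo of 3.0 is regarded as clinically meaningful".

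**Assumptions, because the documents give no value**
- Complete-data degrees of freedom v0 = 122 − 3 = 119 (two treatment means and a baseline slope at Visit 6). A value of 80 is shown as a low alternative; the per-protocol set is smaller by an unknown amount.
- Share of the variance due to missing data, g = (1 + 1/m)B/T, where B is the between-imputation and T the total variance: 0.03 to 0.15, with 0.01 to 0.30 as a wider range.

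**The plan's own figure.** The SAP states no degrees of freedom or quantile for the MI analysis. Its sample size does reproduce: a t test with difference 3.0, SD 5.8 and 60 per arm has 80.2% power (59 per arm: 79.6%). This confirms the planning inputs and does not otherwise bear on the point.

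**Pooled degrees of freedom**
- As written: df = (m − 1)/g² = 99/g².
- With `EDF=` v0: df = 1/(g²/99 + 1/v_obs), where v_obs = [(v0 + 1)/(v0 + 3)] × v0 × (1 − g).
- Example, g = 0.15 and v0 = 119: as written 99/0.0225 = 4,400. With `EDF=`, v_obs = (120/122) × 119 × 0.85 = 99.5, so df = 1/(1/4,400 + 1/99.5) = 97.3.

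| v0 | g | df as written | quantile | df with `EDF=` | quantile | added width | p = 0.050 as written becomes |
|---|---|---|---|---|---|---|---|
| 119 | 0.01 | 990,000 | 1.960 | 115.9 | 1.981 | 1.06% | 0.0524 |
| 119 | 0.05 | 39,600 | 1.960 | 110.9 | 1.982 | 1.10% | 0.0525 |
| 119 | 0.15 | 4,400 | 1.961 | 97.3 | 1.985 | 1.23% | 0.0528 |
| 119 | 0.30 | 1,100 | 1.962 | 76.3 | 1.992 | 1.50% | 0.0534 |
| 80 | 0.01 | 990,000 | 1.960 | 77.3 | 1.991 | 1.59% | 0.0536 |
| 80 | 0.30 | 1,100 | 1.962 | 52.1 | 2.007 | 2.27% | 0.0551 |

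At g = 0.03 and v0 = 119, df is 110,000 as written and 113.4 with `EDF=`, a width ratio of 1.0108. Over g = 0.03 to 0.15 the added width is therefore 1.1–1.2%.

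**On the score scale.** With 61 per arm, SE = 5.8 × √(2/61) = 1.050. The half-width is 2.058 with the normal quantile and 2.080 with t on 119 df, a gap of about 0.02 points on a 0–36 scale.

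**Actual rejection rate.** The last column takes the pooled standard error as correct. Under placebo-based imputation that is doubtful for the treatment difference, so the null rejection rate was simulated. Common settings, all assumed: 61 per arm and within-patient correlation 0.6. Set A used SD 5.8, monotone random dropout after Visit 4, sequential placebo regression, 50 imputations, ANCOVA at Visit 6 in place of the MMRM, and 3,000 runs (Monte Carlo error about 0.3–0.4 points). Set B was a separate simulation of placebo-based imputation.

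| Set | dropout | pooled SE / empirical SE | rejection without `EDF=` | with `EDF=` |
|---|---|---|---|---|
| A | 4% | 1.02 | 4.4% | 4.2% |
| A | 10% | 1.08 | 3.6% | 3.5% |
| A | 15% | 1.13 | 3.0% | 2.9% |
| B | 2% | – | 5.4% | 5.1% |
| B | 5% | – | 4.2% | 4.2% |
| B | 10% | – | 3.8% | 3.8% |
| B | 15% | – | 3.0% | 2.8% |

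**The case against.** The strongest case against the point is about direction. In set A the pooled standard error for the difference was 2–13% too large, more than the 1.1–1.2% of width that the missing option removes. The test as coded stayed below 5% from 4% dropout upwards, and `EDF=` moved it slightly further below. This stands. A reader might infer from the quantiles that the analysis has a true error rate of about 5.25–5.28%. The documents do not support that, because the figure requires a correct standard error, and Rubin's variance is conservative for the treatment difference here. Only at 2% dropout did the simulated rate reach about 5% (5.4% without the option, 5.1% with it).

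A reader might also infer that a result could be significant in the MI analysis and non-significant in the primary. At the same t of 1.970, p is 0.0488 with the near-normal reference and 0.0512 at 119 df. But this needs |t| between about 1.960 and 1.980, the imputation will normally move the estimate, and the SAP attaches no pass/fail rule to the MI p-value. The confirmatory MMRM is untouched.

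Finally, the code is a template: it has placeholders and no by-visit processing, although by-visit results are promised. That weakens the point without removing it. The SAP says these statements will be used, and it writes the degrees-of-freedom option out in full in the MMRM code.

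**Conclusion.** The point holds as a minor technical correction. As printed, the pooled MI results carry thousands of degrees of freedom or more, where a completed dataset offers about 119. For a given pooled standard error, the intervals are about 1.1–1.2% narrower than the small-sample reference (1.6–2.3% with 80 complete-data degrees of freedom and g from 0.01 to 0.30), and p = 0.050 as written corresponds to about 0.052–0.055. No inflated error rate should be claimed: for the treatment difference the overall test is likely at or below 5% except with very little missing data.

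This rests on the software's infinite default, on complete-data degrees of freedom inferred from the FAS size, and on an assumed range for the missing-information share. The amount of missing Visit 6 data within the FAS is not given; the SAP says only that overall dropout was below 15%. The simulated rates rest on the assumed correlation and dropout pattern.

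**What to change.** Add `EDF=` to the PROC MIANALYZE statement. Set it to the Kenward-Roger degrees of freedom of the relevant LS mean or LS-mean difference, averaged over the imputed datasets, and run it separately by visit and by analysis set. State this in section 5.5.1 beside the code. The MI and primary results then differ only through the missing-data assumption.

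The cost is one option and the retention of a degrees-of-freedom value that the MMRM already produces. No new data are needed and the primary test does not change. The downside is intervals 1–2% wider in an analysis that is already somewhat conservative for the treatment difference.
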